## 6.2. SECOND AIM

*Detect differences between eloquent/functional and non-eloquent/non-functional brain areas.*

The Regions Of Interest (ROI) for multispectral/hyperspectral acquisition will be delineated on both peri-operative images (MRI scan) and intra-operative images as extrapolated from the intra-operative videos. For the purpose of this subsection, we will focus our analysis on the comparison between a supposed eloquent area and its surrounding brain tissue. In order to achieve this, we will consider to perform multispectral/hyperspectral acquisition on patients undergoing surgery with neurophysiology monitoring - Motor Evoked Potentials (MEP), SomatoSensory Evoked Potentials (SSEP), Visual Evoked Potentials (VEP), Auditory Evoked Potentials (AEP) - , and/or in patients undergoing awake surgery.

The presence of eloquent brain tissue will be confirmed both anatomically by identifying it on peri-operative and intra-operative assessment, and through neuromonitoring stimulation and/or the execution of a single task during awake surgery, as standard clinical practice in surgery for brain tumours in eloquent areas. From this point of view, clinical correlation with the patient's pre-operative neurological status is crucial in order to consider potential variations in the strength of the intra-operative signal and activation pattern of the analysed eloquent areas – example: a patient with a pre-operative limb weakness is expected to show a different level of activation and therefore might show a different spectroscopic signal compared to a patient with normal motor power. We will also need to take pictures and/or videos of the surgery in order to correlate the expected anatomical location of an eloquent area with the intra-operative finding. The surgical field is limited to the area under the microscope or endoscope magnification, therefore no identifiable pictures or videos will be taken at any point during the study.

Same tests as section 6.1 will be run to statistically validate the data.

### 6.3. THIRD AIM

*Test whether the combination of multispectral/hyperspectral analysis and fluorescence could provide useful new insight into the detection of different perfusion patterns of brain tumours VS normal brain tissue*

Multispectral/hyperspectral imaging will be tested to check whether it can increase the distinction of the fluorophore signal compared with the background. Dedicated statistical software will be used for this analysis.

Each image set will be analysed separately because there will be variability between patients and we will not be able to fully account for this with the limited number of datasets that we are going to record (a well-known problem with many biophotonics/optical techniques). This will all be done offline after the surgery is complete, with a primary aim is to observe whether the technique is capable of detecting changes in the tissue.

We will collect spectral data up until the statistical model used for multivariate analysis does not longer improve the degree of accuracy. We will aim to recruit approximately 50 patients with diagnosis of neuro-oncological disease. Each patient will have an average acquisition of 6 datasets. As each dataset will correspond to an image, this will be divided into many reading regions (from 10 to 20) for a total of approximatively 60 measurements per patient. Based on this estimation, we approximate that 50 patients will provide a spectral database of 3.000 spectra, which we calculate is adequate for diagnostic validation purposes [14].

Same tests as section 6.1 will be run to statistically validate the data.

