## 2. STUDY OBJECTIVES

The present study aims to investigate the potential application of multispectral analysis, hyperspectral imaging, and fluorescence during neurosurgical procedures, specifically during brain tumour resection. The research procedure consists of images acquisition and data processing, with virtually no additional invasive procedures to be performed on patients.

*Study aims:*

- 1) detect structural differences between brain tumour tissue and surrounding brain;
- 2) detect structural differences between eloquent/functional and non-eloquent/non-functional brain areas;
- 3) test whether the combination of multispectral/hyperspectral analysis and fluorescence could provide additional information about the structural differences of brain tumours VS normal brain tissue.

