#### Secondary outcome measures:

The secondary outcome measure will be the analysis of spectroscopic signal reading of surgical field as seen at its baseline and under fluorescence-specific light.

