## 4. PARTICIPANT ENTRY

The present project consists of a pilot observational study on patients diagnosed with brain tumours candidate for a neurosurgical operation.

Patients will be recruited following the inclusion criteria: any patient with a diagnosis of brain tumour, age ranging from 18 with no upper limit, who will agree to the operation and to take part of the present study, will be enrolled.

The present study will include:

- In vivo microscopic and/or endoscopic multispectral/hyperspectral analysis;
- In vivo microscopic and/or endoscopic fluorescence (using either infrared light - IR - or ultraviolet light, depending on the clinical indication of the specific case);

- In vivo microscopic and/or endoscopic fluorescence combined with multispectral/hyperspectral analysis.

Enrolment will proceed for 3 years, with the possibility of stopping the research at an earlier date if a sufficient amount of data is collected for a reliable statistical analysis. From a practical point of view, participation in the study will only imply that some images will be acquired during surgery and processed at a later stage. The study won't impact on patients' care at any stage, nor will produce results that will be relevant for future medical records of patients enrolled. Patients will be approached about this study at the time of their first neuro-oncology clinic consultation – this might not necessarily be the clinic where the diagnosis will be given for the first time, as these patients are often referred from other centres where the diagnosis has already been communicated. A member of the research team who is also involved in direct care will be present at the time of the consultation and will explain in details what are the purposes and the methods of the present study. The patient will be given a PIS at this point.

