## 6.1. FIRST AIM

*Detect structural differences between brain tumour tissue and surrounding brain.*

The Regions Of Interest (ROI) for multispectral/hyperspectral acquisition will be delineated on both peri-operative images (MRI scan) and intra-operative images as extrapolated from the intra-operative videos. We will focus our analysis on three main regions:

- normal brain tissue - brain tissue not infiltrated by tumour or edema, nor grossly pathological on pre-operative images or intra-operative images;
- suspected infiltrated brain tissue – tissue surrounding the tumour where there is strong radiological and clinical suspicion of infiltrative disease or edema;
- tumour tissue – margins and core of the tumour on pre-operative images and intra-operative findings.

The signal in one region of the tumour will be compared to a neighbouring 'healthy' region. The signal itself will come from a processed set of images of the brain, where we will fit the data using one of our established models to extract an indication of tissue oxygenation (as a %) on a per-pixel basis.

The comparison between the set of readings obtained from normal brain will be performed using Principal Component Analysis (PCA) and Linear Discriminant Analysis (LDA) or more advanced techniques including, for example, machine learning. Statistics will be collected on accuracy, sensitivity, specificity, ROC analysis.

We will also need to take pictures and/or videos of the surgical field in order to correlate the expected anatomical location of the tumour and infiltrated areas with the intra-operative finding. The surgical field is limited to the area under the microscope or endoscope

magnification, therefore no identifiable pictures or videos will be taken at any point during the study.

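### Aim 3 asks what combining spectral imaging with fluorescence adds on tumour versus normal brain, but the one test specific to it in section 6.3 is fluorophore against an undefined background

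*Combined protocol and SAP*

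**What the plan says.** Aim 3 is described in four places in the combined protocol and SAP.

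- **Section 2 (Study objectives).** The combination of spectral analysis and fluorescence is tested for whether it "could provide additional information about the structural differences of brain tumours VS normal brain tissue". The classes are tissue types, and the question is about an increment.
- **Section 6.3, heading.** The combination "could provide useful new insight into the detection of different perfusion patterns of brain tumours VS normal brain tissue". The two tissue classes are the same as in section 2; the feature changes from structure to perfusion.
- **Section 6.3, text.** "Multispectral/hyperspectral imaging will be tested to check whether it can increase the distinction of the fluorophore signal compared with the background". Neither fluorophore signal nor background is linked to a tissue label. The section ends: "Same tests as section 6.1 will be run to statistically validate the data".
- **Section 3.1 (Secondary outcome measures).** The outcome is the "analysis of spectroscopic signal reading of surgical field as seen at its baseline and under fluorescence-specific light". No tissue class or reference is named.

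The tests carried over from 6.1 are PCA with LDA, or more advanced techniques such as machine learning, and "Statistics will be collected on accuracy, sensitivity, specificity, ROC analysis". Section 6.1 also defines region labels: normal brain, suspected infiltrated brain, and tumour.

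**The concern.** In the aim, the target condition is tumour. In the test that 6.3 describes, it is the presence of fluorophore. Sensitivity, specificity and ROC curves have a meaning only relative to a stated target condition, so an analyst working from 6.3 could reasonably compute them for dye against no dye. A second analyst, working from the heading, could compute them for tumour against normal brain. The two sets of results would not be interchangeable.

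The aim also asks for added information, and 6.3 names no comparator for the tissue question. It does not say whether the combined signal is set against fluorescence alone, spectral imaging alone, or both.

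At stake is what may be concluded. If dye contrast improves and that is all that was measured, the study has shown a better view of dye. It has not shown a better separation of tumour from brain, which is what section 2 asks and what section 7 hopes to build a surgical guidance tool on.

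**Working it through.** **The plan's own figure.** The only sample-size figure in 6.3 is a database of 3,000 spectra. It reproduces as 50 patients × 6 datasets × 10 regions = 3,000, which is the low end of the stated 10 to 20 regions; 20 regions would give 50 × 6 × 20 = 6,000. No target AUC, effect size or error rate accompanies it, so it does not show which contrast the study is sized for. The point here does not depend on it.

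**Does the reference to 6.1 settle the classes?** The identical closing sentence appears in 6.2, where the classes are eloquent and non-eloquent brain. It therefore carries over methods and statistics; the classes have to come from the section in which it stands. In 6.3 that section offers two candidates: tumour versus normal brain in the heading, and fluorophore versus background in the text. The reference does not choose between them.

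**When are the two contrasts the same?** Inputs, none of which the documents give, so all are assumptions:

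- A = AUC for fluorophore versus background
- s = share of tumour regions with dye
- f = share of normal-brain regions with dye
- the score depends on tissue only through dye

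Take one tumour region and one normal region at random.

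- Tumour has dye and normal does not: probability s(1−f), and tumour scores higher with probability A.
- Normal has dye and tumour does not: probability (1−s)f, and tumour scores higher with probability 1−A.
- Both have dye or both lack it: probability sf + (1−s)(1−f), and tumour scores higher with probability 0.5.

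AUC(tumour vs normal) = s(1−f)A + (1−s)f(1−A) + 0.5[sf + (1−s)(1−f)]

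Because s(1−f) − (1−s)f = s − f, this simplifies to

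AUC(tumour vs normal) = 0.5 + (A − 0.5) × J, with J = s − f.

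For a rise in A from 0.85 to 0.95:

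| J | At A = 0.85 | At A = 0.95 | Gain |
|---|---|---|---|
| 1.0 | 0.5 + 0.35 × 1.0 = 0.85 | 0.5 + 0.45 × 1.0 = 0.95 | 0.10 |
| 0.8 | 0.5 + 0.35 × 0.8 = 0.78 | 0.5 + 0.45 × 0.8 = 0.86 | 0.08 |
| 0.6 | 0.5 + 0.35 × 0.6 = 0.71 | 0.5 + 0.45 × 0.6 = 0.77 | 0.06 |
| 0.2 | 0.5 + 0.35 × 0.2 = 0.57 | 0.5 + 0.45 × 0.2 = 0.59 | 0.02 |
| 0 | 0.50 | 0.50 | 0 |

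Under this model the contrasts coincide only at J = 1, when every tumour region and no normal region carries dye. Nothing in the documents states that. Section 4.3 admits any intrinsic or extrinsic tumour, primary or secondary, and section 4 has fluorescence done "using either infrared light - IR - or ultraviolet light, depending on the clinical indication of the specific case", so a single value of J across cases cannot be taken for granted.

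**The case against.** The strongest reply is that 6.3 has not left its aim. Its heading names tumour and normal brain, and in 6.2 the same closing sentence takes its classes from that section's own heading and text. Applied here, the 6.1 statistics could be run on tumour versus normal brain, with the fluorophore check as a technical step beforehand. That reading is possible, and it rules out saying that 6.3 abandons the tissue contrast. It is not secure, because the text under the heading names a different contrast and nothing ranks the two.

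Three stronger readings are tempting, and the documents do not support them.

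- A reader might infer that section 3.1 gives a further, competing definition. It describes which readings are taken, and those are data that a comparison for Aim 3 would use. It lacks a tissue class, which is under-specification rather than a rival target.
- A reader might infer that Aim 3 could be declared a success on dye contrast. There is no success criterion, threshold or hypothesis test for Aim 3. Section 6.3 speaks of observing whether the technique can detect tissue changes, and section 3 calls the study a pilot.
- A reader might take the AUC figures as a forecast or a ceiling for the combined signal. They assume that tissue acts only through dye, whereas sections 1.2 and 6.1 expect spectra to carry tissue information of their own, such as oxygenation. If they do, the combined signal can exceed these values.

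**Conclusion.** The concern holds as a mismatch between the aim (section 2 and the 6.3 heading) and the one aim-specific test in the 6.3 text, which neither the reference to 6.1 nor section 3.1 clearly resolves. The test as described can show clearer dye without showing any gain in telling tumour from brain.

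The size cannot be known from the documents, which say nothing on how dye is distributed between tumour and normal brain. Under the dye-only assumption, a 0.10 gain in fluorophore AUC is worth between 0.08 (J = 0.8) and 0.02 (J = 0.2) on the tissue contrast. These values show that the two contrasts can part widely; they do not predict this study's results.

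Severity is low to moderate. The outcome is secondary, the study is a pilot, and no formal decision rests on Aim 3. The correction is nonetheless specific and cheap.

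**What to change.** In sections 3.1 and 6.3, state the Aim 3 analysis as the change in discrimination between tumour and normal-brain regions:

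- **Labels:** the tumour and normal-brain regions of 6.1.
- **Statistics:** those already listed in 6.1 (accuracy, sensitivity, specificity, ROC).
- **Comparison:** the combined signal against fluorescence alone, and against spectral imaging alone.
- **Pairing:** the same regions under each signal, compared within patient. This fits the plan's own reasoning that "Each image set will be analysed separately because there will be variability between patients".

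Keep fluorophore-to-background contrast as a descriptive technical measure, and say that it does not by itself support a conclusion about tumour versus brain.

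The cost is a little more offline analysis. Section 4 already lists spectral imaging, fluorescence and their combination, and the region labels are already planned. Section 4 does not say that every patient will have all three, so the paired comparison may rest on fewer than 50 patients, and that number should be reported. Aim 3 performance may also look less favourable than dye contrast would.

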Surgery will be conducted following standard procedures, already validated in clinical practice. The surgeons performing the procedures will be [name] [name] (CI), [name] (PhD student and clinical fellow), [name] (Consultant Neurosurgeon), and [name] (Neurosurgery Trainee and Clinical Lecturer). Surgeons will work in teams, each team with no more than two surgeons. [name] and one of his collaborators will be present in theatre to facilitate images acquisition. For each researcher not normally involved in clinical practice, research passport will be provided. Intra-operative imaging data and spectra will be collected during tumour resection, but the analysis on the spectra will be performed on a different time and setting, in order not to excessively prolong the surgical procedure.

Researchers will collect spectral data up until the statistical model used for multivariate analysis does not longer improve the degree of accuracy (see Section 6 - statistical analysis).

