## 10. PUBLICATION POLICY

This study will follow the Imperial College of London publication policies and anti-plagiarism guidelines. Non-identifiable data will be used during publication. Authorships and authors order will be defined in due course. We will collect spectral data up until the statistical model used for multivariate analysis does not longer improve the degree of accuracy.

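### Section 6.3 treats 3,000 spectra as enough for diagnostic validation, but the plan never tests a classifier on patients kept out of the fitting

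*Combined protocol and SAP*

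**What the plan says.** Section 6.3 (third aim) makes three statements about how the spectra will be used.

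- Unit of analysis: "Each image set will be analysed separately because there will be variability between patients". The reason continues: "we will not be able to fully account for this with the limited number of datasets that we are going to record". The stated purpose is modest: "to observe whether the technique is capable of detecting changes in the tissue".
- Size: "50 patients will provide a spectral database of 3.000 spectra, which we calculate is adequate for diagnostic validation purposes", with one literature reference in support.
- Stopping: collection continues until model accuracy stops improving. Section 4.1 repeats this ("Researchers will collect spectral data up until the statistical model used for multivariate analysis does not longer improve the degree of accuracy"), as does section 10. Section 4 also allows an earlier end, "with the possibility of stopping the research at an earlier date if a sufficient amount of data is collected for a reliable statistical analysis".

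Section 6.1 names PCA with LDA, or more advanced methods such as machine learning, and promises accuracy, sensitivity, specificity and ROC results. Sections 6.2 and 6.3 carry the same tests to aims 2 and 3. Section 6.1 also says that the tumour signal is compared with a nearby region taken as healthy.

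The available text does not say which readings fit a classifier and which test it. It mentions no cross-validation and no held-out patients.

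**The concern.** Analysing each image set on its own suits the feasibility question of whether the technique sees any change in the tissue. It cannot show that a classifier built on some patients works in the next one, and that is what diagnostic validation means. The 3,000 spectra exist only as a sum over patients, and readings from one patient resemble each other. If patient variability stands in the way of a joint analysis, that sum does not establish adequacy. If a joint analysis is intended, the plan must say how patients are kept apart between fitting and testing.

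Two things depend on the answer: what the reported accuracy figures may be said to show, and when collection stops, because the stopping rule uses an accuracy whose source is not defined.

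The unit is also unclear. Section 6.3 says "As each dataset will correspond to an image", while section 6.1 speaks of a signal derived from several processed images, so an image set could be one image or all images of a patient.

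**Working it through.** **1. The plan's own total.** Inputs from section 6.3: 50 patients, 6 images per patient on average, 10 to 20 regions per image.

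50 × 6 × 10 = 3,000, or 60 per patient. The stated figure is reproduced at the lower end of the range; 20 regions would give 50 × 6 × 20 = 6,000. The arithmetic is not at fault.

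**2. What 3,000 correlated readings are worth.** The documents give no intraclass correlation (ICC), so a range is assumed. Design effect = 1 + (60 − 1) × ICC; effective N = 3,000 / design effect; 95% half-width at an assumed accuracy of 0.80 = 1.96 × √(0.80 × 0.20 / effective N).

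| ICC | Design effect | Effective N | Half-width |
|---|---|---|---|
| 0 | 1.00 | 3,000 | 0.014 |
| 0.1 | 6.90 | 435 | 0.038 |
| 0.3 | 18.7 | 160 | 0.062 |
| 0.5 | 30.5 | 98 | 0.079 |

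**3. Splitting spectra at random against leaving patients out.** Simulation with assumed variances: 50 patients × 6 images × 10 readings; SDs of 1.0 (patient), 0.5 (image) and 1.0 (error) in every feature. Each patient also has an independent offset for each tissue class, with SD s from 0.3 to 1.0, so the patient's tumour-minus-normal difference has SD √2 × s, or 0.42 to 1.41. There are two equally frequent classes and no shared tumour signal, so true accuracy is 0.50. LDA, 10-fold cross-validation.

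| Input to LDA | Random split of spectra | Left-out patients |
|---|---|---|
| 1 feature | 0.50–0.52 | 0.49–0.51 |
| 30 bands, PCA to 3–5 components | 0.50–0.54 | 0.50 |
| 10 features | 0.51–0.57 | 0.50 |
| 30 features, no PCA | 0.52–0.62 | 0.50–0.51 |

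Machine learning on 10 features (only four runs per setting, so rough) gave 0.54 to 0.77 under the random split, against 0.49 to 0.51 on left-out patients.

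These ranges are illustrations, not bounds. If s is read as the SD of the tumour-minus-normal difference, the upper values for 10 and 30 features fall to about 0.55 and 0.59. Centring readings within each image raises them to about 0.60 and 0.68.

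**4. Scoring on the fitted readings.** Pure noise, balanced classes, LDA scored on the readings that fitted it:

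| Readings | 1 feature | PCA to 3 of 30 bands | PCA to 5 of 30 bands |
|---|---|---|---|
| 10 | 0.61 | 0.74 | 0.85 |
| 20 | 0.57 | 0.65 | 0.71 |
| 60 | 0.54 | 0.58 | 0.62 |

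Ten to 20 readings is what one image supplies under section 6.3.

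**5. The stopping rule.** Same model with s = 0.7 and a real shared shift of 1 SD in one feature; accuracy at 10 and at 50 patients:

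| Input to LDA | Random split | Left-out patients |
|---|---|---|
| 1 feature | 0.626 → 0.620 | 0.620 → 0.619 |
| 30 bands, PCA to 5 components | 0.557 → 0.553 | 0.531 → 0.542 |
| 10 features | 0.669 → 0.628 | 0.572 → 0.605 |

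With one feature the curves practically coincide, and with PCA to 5 components the gap is small. With 10 features the random-split curve falls while accuracy in new patients is still rising, so a rule that stops when accuracy no longer improves could stop too early.

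**The case against.** A reader might infer that section 6.3 flatly contradicts itself for the whole study. The documents do not support that. The separate-analysis sentence follows the text on fluorophore signal under aim 3, while the paragraph on 50 patients and the stopping rule reads as study-wide. Image sets could be analysed separately for aim 3 while one model is built across patients for aim 1. This limits the conflict to an unclear scope. It does not supply a test on held-out patients for either reading.

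Second, section 6.1 compares tumour with a neighbouring healthy region, which may remove part of the patient variability. This stands as a limit on the remedy: a rule forbidding any use of tissue labels from the held-out patient could bar the plan's own comparison. Such referencing should be allowed, but declared. It does not make the validation unit clear.

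Third, for PCA with LDA, the first methods named, random-split inflation is small. That is correct. But the plan fixes neither the number of features nor the classifier, and it allows machine learning.

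Fourth, this is a pilot whose stated purpose is feasibility, and adequacy rests on a reference that was not available here. The pilot status lowers the severity. A sample-size reference would not by itself say which patients test the model.

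**Conclusion.** The point holds in a limited form. The plan attaches a diagnostic-validation claim to a total of correlated readings and describes no test on patients outside the fitting. As written, neither its accuracy figures nor its stopping rule show performance in a new patient.

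A reader might go further and infer that the reported accuracy will be heavily inflated. The documents do not support that: they do not say that spectra will be split at random, that accuracy will be scored on the fitted readings, or that all spectra enter one model. Under the assumed variances, a random split adds almost nothing with one feature, about 0.04 at most with PCA to 3 to 5 components, and about 0.12 with 30 raw features; flexible methods can add more. The largest distortion, 0.71 to 0.85 for pure noise, arises only if a single image is scored on its own readings with 5 components. The stopping rule is clearly affected only with many features.

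Severity is low to moderate. The study is a pilot, and section 4 says that it does not influence care. The absence of a validation scheme is established for the available text only.

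**What to change.** Add to section 6:

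> Results from within one image or one patient are descriptive feasibility results. Any accuracy, sensitivity, specificity or AUC offered as diagnostic validation, and the accuracy used in the stopping rule, comes from leave-one-patient-out or patient-grouped cross-validation, with scaling, PCA, choice of classifier and tuning done inside the training patients. If readings are referenced to a neighbouring healthy region of the same patient, this is stated, and the accuracy is described as conditional on that region being known.

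Define an image set and state which aims the separate analysis covers. If patient-grouped validation is not intended, delete the claim in section 6.3 that the database suffices for diagnostic validation.

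The cost is wording and modest computing, with no new data. Reported accuracy will probably be lower and less precise, because the test unit becomes the patient. In the simulation with a real shift and 50 patients, left-out-patient accuracy varied between studies with SD 0.019 to 0.023, so about ±0.04 to 0.05 (1.96 × SD). Treating 3,000 readings as independent would suggest √(0.60 × 0.40 / 3,000) = 0.009, or about ±0.02. The figure of about 50 patients applies to aim 1 only. Aim 2 depends on patients having neurophysiology monitoring or awake surgery, and the documents give no number for them; the same may hold for aim 3, where the fluorescence light used depends on the clinical indication.

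### Without a same-tissue reference or a defined failing result, a difference found within one image cannot be attributed to tumour or eloquent tissue

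*Combined protocol and SAP*

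**What the plan says.** Section 6.1 fits a model to each set of images to "extract an indication of tissue oxygenation (as a %) on a per-pixel basis". The contrast is then local: "The signal in one region of the tumour will be compared to a neighbouring 'healthy' region". The methods are PCA with LDA, or machine learning, summarised by accuracy, sensitivity, specificity and ROC analysis.

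Section 6.2 concerns "the comparison between a supposed eloquent area and its surrounding brain tissue", and Section 6.3 asks "whether it can increase the distinction of the fluorophore signal compared with the background". Both reuse the tests of 6.1.

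Section 6.3 alone adds the unit of analysis: "Each image set will be analysed separately because there will be variability between patients". It describes the purpose as "to observe whether the technique is capable of detecting changes in the tissue". The same section also plans a database of 3,000 spectra for diagnostic validation, and a multivariate model whose accuracy is followed until it stops improving. Both imply pooling over patients.

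No section gives a significance level, a performance threshold, a result that would count as failure, or an explicit contrast between two patches of the same tissue. One sentence in 6.1 refers to comparing readings from normal brain but names no second set. It appears incomplete.

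**The concern.** In a single image the tumour patch and the healthy patch lie in different places. They can differ in local vessels, surface curvature and lighting as well as in tissue type. Two patches of normal brain differ in those same respects. Unless one knows what the pipeline returns for two patches of one tissue, a difference between tumour and neighbour has no reference.

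Sensitivity, specificity or AUC computed within the image does not solve this. They measure how separable two patches are, not why. Cross-validation inside the image does not help either, because the training and test pixels share the same two positions.

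At stake is the study's main claim. Section 7 hopes for a benchmark towards a tool that guides resection. A count of images in which a difference was seen could not support that hope, because the plan does not say how many such images to expect if tissue type had no effect.

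**Working it through.** **The plan's own count.** 50 patients × 6 images × 10 regions = 3,000 spectra, as stated in Section 6.3. This uses the lower end of the 10 to 20 regions per image; 20 regions would give 6,000.

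**Inputs for the check.** Splitting 10 to 20 regions into two patches gives m = 5 to 10 readings per patch. Because 6.1 works per pixel, m = 1,000 is also shown (assumed). The share of total variance lying between patches of the same tissue, ρ, is not in the documents; the range 0.05 to 0.5 is assumed. A two-sided 5% test is also assumed, since the plan names none.

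**Two normal patches, naive two-sample test.** The variance of the difference is understated by the factor V = 1 + mρ/(1 − ρ). The chance of declaring a difference is P(|t| > c/√V), where t has 2m − 2 degrees of freedom and c is its 5% critical value.

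- m = 5, ρ = 0.05: V = 1 + 5 × 0.05/0.95 = 1.263, c = 2.306, c/√V = 2.05, giving 0.074.
- m = 10, ρ = 0.5: V = 1 + 10 × 0.5/0.5 = 11, c = 2.101, c/√V = 0.63, giving 0.534.
- m = 1,000, ρ = 0.05: V = 53.6, c/√V = 0.27, giving 0.789.
- m = 1,000, ρ = 0.5: V = 1,001, c/√V = 0.06, giving 0.951.

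| ρ | m = 5 | m = 10 | m = 1,000 |
|---|---|---|---|
| 0 | 5% | 5% | 5% |
| 0.05 | 7% | 11% | 79% |
| 0.1 | 10% | 17% | 85% |
| 0.3 | 23% | 37% | 93% |
| 0.5 | 37% | 53% | 95% |

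With no patch effect at all, 50 × 6 = 300 images would still yield about 300 × 0.05 = 15 chance differences.

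**Within-image AUC.** Cross-validated LDA on three components was simulated for two normal patches (400 runs per setting). At 1,000 pixels per patch the median AUC was 0.63, 0.70, 0.83 and 0.94 for ρ = 0.05, 0.1, 0.3 and 0.5. At ρ = 0 it was about 0.5. A good AUC can therefore arise with no tissue difference.

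**Can a single image be judged against its own normal pairs?** Not reliably. With one tumour patch T and two normal patches N1 and N2, all exchangeable under the null, |T − N1| exceeds |N1 − N2| half the time. With k normal regions, a rank rule cannot have an error rate below 1/(k + 1). If all but one of the 10 to 20 regions were normal, that is 1/10 to 1/20.

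**Patient-level excess.** One value of |T − N1| − |N2 − N1| was simulated for each of 50 patients (10 readings per patch, 4,000 runs per setting). A one-sided 5% test rejected in 4.6% to 5.5% of null runs. For a true shift of 0.5 total SD, power was 0.77 at ρ = 0.05 and 0.19 at ρ = 0.5. Requiring a two-sided 95% interval to lie above zero is a one-sided 2.5% test. Rerunning the simulation at that level (20,000 runs) gave power of 0.67 down to 0.11. By comparison, a signed mean difference per patient, T − (N1 + N2)/2, tested two-sided at 5%, had power 0.97 to 1.00 at 0.5 SD and 0.33 to 0.85 at 0.2 SD.

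**The case against.** A reader might infer that the plan's test cannot fail, or that almost any two patches of brain will look different. The documents support neither.

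- The planned accuracy, specificity and ROC figures could be poor. A pooled model over 3,000 spectra, tested on patients it had not seen, could fail outright, because random patch effects have no consistent pattern across patients.
- The high false-positive rates need pixel-level analysis or strong patch effects. Section 6.3 counts regions, not pixels, and at 5 to 10 readings per patch with ρ = 0.05 the rate is only 7% to 11%.
- The separate-analysis sentence is in 6.3 only. Reusing the tests of 6.1 there does not carry that rule back to aims 1 and 2.
- Aim 3 asks about fluorophore against background, and the secondary outcome in Section 3.1 views the surgical field at baseline and under fluorescence light. This partly holds position fixed.
- Section 3.1 correlates the signal with the operative view, MRI and neurophysiology, and Section 4.1 adds histology.
- This is a pilot study, analysed offline, with no effect on care.

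These points limit the size and reach of the concern, but they do not remove it. MRI, neurophysiology and histology improve the tissue labels; they do not separate label from position. The missing same-tissue reference affects 6.1 and 6.2 on their own wording, since both contrast only neighbouring regions labelled different. The incomplete normal-brain sentence in 6.1 might have been meant as a control, but it cannot be relied on as one until clarified. The pooled reading conflicts with the per-image statement in the same section, and the plan does not say which governs.

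**Conclusion.** The concern holds in this form: following the plan as written can produce a positive finding that cannot be attributed to tissue type, and no result is named that would count against the technique. The confounding of tissue with position follows from the design of the contrasts and needs no assumed figure.

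Its size does rest on assumptions. For ρ between 0.05 and 0.5, false differences between two normal patches run from about 7% to 53% with 5 to 10 readings per patch, and from about 79% to 95% with 1,000 pixels, treating readings within a patch as independent. The stronger claim, that a positive answer is guaranteed, does not follow: at the low end of that range most normal pairs would not test as different, and the planned performance measures could disappoint. For a pilot observational study this should be fixed before analysis; it is not a fatal flaw.

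**What to change.** 1. State for each aim whether analysis is per image or pooled over patients, and complete the sentence in 6.1 on normal-brain readings.
2. In 6.1, and in 6.3 where tumour is compared with normal brain, run the identical pipeline on normal-versus-normal pairs at similar separation in every image with at least two normal regions. In 6.2 use non-eloquent versus non-eloquent pairs. Fix the contrast measure in advance.
3. For each patient, average over images the tumour-normal (or eloquent-non-eloquent) contrast minus the same-tissue contrast. Report the mean excess across patients with a 95% confidence interval, and claim detection only if the interval lies above zero. This also defines a failing result.
4. Do not count single images as detecting a difference because they exceed their own few normal pairs.
5. Validate any pooled classifier with whole patients held out.

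Cost: SAP wording and extra analysis. Images are already divided into 10 to 20 regions, so no new acquisition is needed where normal regions are in view. Images with fewer than two normal regions, probably including some cavity views, give no control, and their number should be reported. Power is lower than a naive per-image test would suggest (0.11 to 0.67 for an assumed 0.5 SD shift with one contrast per patient; averaging over images was not simulated). Matching on separation will not remove a position effect that always favours the tumour side, such as the tumour always lying at the centre of the lit field.
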